7.1 Adverse Event Characteristics

CTCAE term (AE description) and grade: The descriptions and grading scales found in the revised NCI Common Terminology Criteria for Adverse Events (CTCAE) version 5.0 will be utilized for AE reporting. All appropriate treatment areas should have access to a copy of the CTCAE version 5.0. A copy of the CTCAE version 5.0 can be downloaded from the CTEP web site http://ctep.cancer.gov/protocolDevelopment/electronic_applications/ctc.htm.

• **Attribution** of the AE:

- Definite The AE *is clearly related* to the study treatment.
- Probable The AE *is likely related* to the study treatment.
- Possible The AE *may be related* to the study treatment.
- Unlikely The AE *is doubtfully related* to the study treatment.
- Unrelated The AE *is clearly NOT related* to the study treatment.

7.2 Definitions

7.2.1 Adverse Event (AE)

An adverse event (AE) is any untoward medical occurrence (e.g., an abnormal laboratory finding, symptom, or disease temporally associated with the use of a drug) in a patient or clinical investigation subject administered a pharmaceutical product and which does not necessarily have a causal relationship with this treatment. An AE can therefore be any unfavorable and unintended sign (including an abnormal laboratory finding), symptom, or disease temporally associated with the use of a medicinal product, whether or not related to the medicinal product.

Hospitalization for elective surgery or routine clinical procedures that are not the result of an AE (e.g., surgical insertion of central line) need not be considered AEs and should not be recorded as an AE. Disease progression should not be recorded as an AE, unless it is attributable by the investigator to the study therapy.

7.2.2 Suspected Adverse Reaction (SAR)

A suspected adverse reaction (SAR) is any AE for which there is a *reasonable possibility* that the drug is the cause. *Reasonable possibility* means that there is evidence to suggest a causal relationship between the drug and the AE. A suspected adverse reaction implies a lesser degree of certainty about causality than adverse reaction, which means any adverse event caused by a drug.

Causality assessment to a study drug is a medical judgment made in consideration of the following factors: temporal relationship of the AE to study drug exposure, known mechanism of action or side effect profile of study treatment, other recent or concomitant drug exposures, normal clinical course of the disease under investigation, and any other underlying or concurrent medical conditions. Other factors to consider in considering drug as the cause of the AE:

- Single occurrence of an uncommon event known to be strongly associated with drug exposure (e.g., angioedema, hepatic injury, Stevens-Johnson Syndrome)
- One or more occurrences of an event not commonly associated with drug exposure, but otherwise uncommon in the population (e.g., tendon rupture); often more than once occurrence from one or multiple studies would be needed before the sponsor could determine that there is *reasonable possibility* that the drug caused the event.
- An aggregate analysis of specific events observed in a clinical trial that indicates the events occur more frequently in the drug treatment group than in a concurrent or historical control group

7.2.3 Unexpected AE or SAR

An AE or SAR is considered unexpected if the specificity or severity of it is not consistent with the applicable product information (e.g., Investigator's Brochure (IB) for an unapproved investigational product or package insert/summary of product characteristics for an approved product). Unexpected also refers to AEs or SARs that are mentioned in the IB as occurring with a class of drugs or as anticipated from the pharmacological properties of the drug, but are not specifically mentioned as occurring with the particular drug under investigation.

7.2.4 Serious AE or SAR

An AE or SAR is considered serious if, in the view of either the investigator or sponsor, it results

in any of the following outcomes:

- Death;
- Is life-threatening (places the subject at immediate risk of death from the event as it occurred);
- Requires inpatient hospitalization (>24 hours) or prolongation of existing hospitalization;*
- Results in congenital anomaly/birth defect;
- Results in a persistent or significant incapacity or substantial disruption of the ability to conduct normal life functions;
- Important medical events that may not result in death, be life-threatening, or require
 hospitalization may be considered a serious adverse drug experience when, based upon
 appropriate medical judgment, they may jeopardize the patient or subject and may require
 medical or surgical intervention to prevent one of the outcomes listed in the definition.
 For reporting purposes, also consider the occurrences of pregnancy as an event which
 must be reported as an important medical event.

*Hospitalization for anticipated or protocol specified procedures such as administration of chemotherapy, central line insertion, metastasis interventional therapy, resection of primary tumor, or elective surgery, will not be considered serious adverse events.

Pregnancy that occurs during the study must also be reported as an SAE.

7.3 Documentation and Reporting of non-serious AEs or SARs

- For non-serious AEs or SARs, documentation must begin from day 1 of study treatment and continue through the 30 day follow-up period after treatment is discontinued.
- Adverse events grades 1 and 2 if the attribution is at least possibly related to selumetinib. Record all adverse events grades 3, 4 or result in death (Grade 5) (while on treatment or within 30 days of treatment), regardless of attribution on the case report forms.
- Baseline abnormalities: Any baseline (pretreatment) abnormalities observed from the time treatment consent is obtained to the start of trial therapy should be recorded on the case report form.

Collected information should be recorded in the Case Report Forms (CRF) for that patient. Please include a description of the event, its severity or toxicity grade, onset and resolved dates (if applicable), and the relationship to the study drug. Documentation should occur at least monthly.

7.4 SAEs or Serious SARs

7.4.1 Timing

After informed consent but prior to initiation of study medications, only SAEs caused by a protocol-mandated intervention will be collected.

7.4.2 Documentation and Sponsor Notification

For any other experience or condition that meets the definition of an SAE or a serious SAR, recording of the event must begin from day 1 of study treatment and continue through the 30 day follow-up period after treatment is discontinued. All SAEs or Serious SAR (including deaths) regardless of attribution will be recorded in the CRF. The Sponsor must be notified of any SAE or Serious SAR within 24 hours of learning of the event. These events (SAEs or Serious SARs) must also be documented within the CRF for that participant within 2 business days of notification of the Sponsor-Investigator/Study Chair or designee.

7.4.3 Documentation and Assessment

Once an AE is detected with a possible causal relationship to selumetinib, it should be followed until its resolution to baseline or until it is judged to be permanent and stable. Assessment should be made at each visit (or more frequently, if necessary) of any changes in severity, changes to the suspected relationship to the study treatment, the interventions required to treat it, and the outcome.

Progression of malignancy if documented by use of appropriate method (as in section 11.1) should not be reported as a serious adverse event unless results in death.

Deaths (while on treatment or within 30 days of treatment), regardless of attribution will be recorded on the case report forms and reported as an SAE.

Death due to progressive disease should be reported as Grade 5 "Neoplasms benign, malignant and unspecified (including cysts and polyps)-Other (Progressive Disease)" under the system organ class (SOC) of the same name. Evidence that the death was a manifestation of underlying disease (e.g., radiological changes suggesting tumor growth or progression: clinical deterioration associated with a disease process) should be submitted.

7.5 Other Malignancy

7.5.1 Secondary Malignancy

A *secondary malignancy* is a cancer caused by treatment for a previous malignancy (*e.g.*, treatment with investigational agent/intervention, radiation or chemotherapy) is to be reported as an SAE. A secondary malignancy is not considered a metastasis of the initial neoplasm.

Three options are available to describe the event:

- Leukemia secondary to oncology chemotherapy (e.g., acute myelocytic leukemia)
- Myelodysplastic syndrome (MDS)
- Treatment-related secondary malignancy

7.5.2 A Second Malignancy

A second malignancy is one unrelated to the treatment of a prior malignancy (and is **NOT** a metastasis from the initial malignancy) does not need to be reported.

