11 MEASUREMENT OF EFFECT

11.1 Hearing Response Criteria (Stratum 1 only)

Hearing is monitored in clinical practice by measuring pure tone thresholds, word recognition scores, brainstem auditory evoked responses (BAERs), and otoacoustic emissions (OAEs).

Pure tone thresholds measure the minimum sound level that an ear can perceive. Thresholds are typically measured at octaves and half-octaves from 250 Hz to 8000 Hz. An average of thresholds at 500, 1000, 2000 and 4000 Hz (PTA) is recommended as a standard outcome measure by the American Academy of Otolaryngology, Head and Neck Surgery (AAO-HNS) for reporting in cases of VS.

Word recognition scores measure the ability to recognize (as opposed to detect) auditory information. Patients are presented a list of 50 words at a fully audible level and the percentage identified correctly is the score. This study will use full 50-item monosyllable lists and standardized recordings.

Because tumors associated with NF2 have benign histology, overall survival is not an appropriate endpoint for clinical trials in this condition. Instead, the goal of treatment is to minimize neurologic morbidity (including hearing loss) and to defer surgical treatments that may cause iatrogenic dysfunction. For this reason, hearing function is the most important way to monitor the activity of new agents designed to treat VSs.

Word recognition is the measure most closely associated with daily hearing function since it measures the ability to comprehend speech. If word recognition quality improves, the patient can converse successfully, even if a hearing aid is needed to make sounds sufficiently loud. Statistical methods have been developed to determine significant changes in this measure. Word recognition scores represent summary scores from a collection of binary endpoints (correct/incorrect responses) and thus follow a binomial distribution (e.g., non-Gaussian

^{**} Please note that Grade 3 asymptomatic elevations of CPK do not require a dose reduction

distribution). Although it is tempting to use a set change in word recognition score (e.g., fifteen percentage points) as a clinical response, this approach is inappropriate given the binomial model of variance. A more rigorous approach involves the use of the 95% (p=0.05) critical difference table⁴⁴. The 95% critical differences for 50-word lists as proposed here have been used in previous studies⁴⁵ and in clinical trials evaluating the effect of drug treatment on hearing.

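### The reporting waiver for unrelated new cancers in section 7.5.2 conflicts with the all-SAE rule in 7.4.2, and both 7.5 definitions presuppose a prior malignancy

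*Combined protocol and SAP*

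**What the plan says.** Section 7.5 of the protocol divides later cancers into two kinds.

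- Under 7.5.1, a secondary malignancy "is a cancer caused by treatment for a previous malignancy". The examples of treatment and the consequence read: "treatment with investigational agent/intervention, radiation or chemotherapy) is to be reported as an SAE".
- Under 7.5.2, "A second malignancy is one unrelated to the treatment of a prior malignancy". Provided that it is also not a metastasis, it "does not need to be reported". No grade, seriousness criterion or time limit restricts this.

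The general rule for serious events is in 7.4.2: "All SAEs or Serious SAR (including deaths) regardless of attribution will be recorded in the CRF". It continues: "The Sponsor must be notified of any SAE or Serious SAR within 24 hours of learning of the event". On timing, "recording of the event must begin from day 1 of study treatment and continue through the 30 day follow-up period after treatment is discontinued".

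Three other places bear on the point. Section 7.3 asks for all grade 3, 4 and 5 adverse events on the case report form, on treatment or within 30 days, whatever the attribution. Section 7.4.3 asks for every death in the same period to be reported as an SAE. Section 11.1 describes the disease under study: "Because tumors associated with NF2 have benign histology".

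**The concern.** The same event can meet two rules with different outcomes. If site staff follow 7.5.2, a serious new cancer judged unrelated need not be reported. If they follow 7.4.2, it goes on the case report form and to the sponsor within a day. Nothing in the protocol says which section prevails.

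The waiver depends on attribution, and this trial has no control arm. Section 7.2.2 lists, among the grounds for suspecting a causal link, an aggregate analysis of events against a concurrent or historical control group. Such an analysis needs all cases counted, including those first judged unrelated. Participants may be as young as 3 (section 3.1.4) and may take the drug for 26 courses (section 5.5), so new cancers are events that the sponsor and the DSMB would want to see in full.

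The definitions raise a second difficulty. Both 7.5 categories depend on an earlier malignancy, in a population enrolled for benign tumours.

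**Working it through.** No arithmetic applies: the point depends on no rate, error level or sample size. The check is to set the sections side by side.

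**Step 1. Does the general SAE rule reach a new cancer?** Section 7.2.4 makes an adverse event serious on death, threat to life, hospital stay over 24 hours, lasting incapacity, congenital anomaly, or medical judgement that it is an important medical event. None of these refers to a prior malignancy. A new cancer is not listed as serious in itself, but it can meet one or more of these criteria.

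**Step 2. Apply each rule to a new cancer judged unrelated to earlier treatment, arising from day 1 to 30 days after treatment.**

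| Event | General rules | Section 7.5.2 | Result |
|---|---|---|---|
| Meets a 7.2.4 criterion | 7.4.2: record it, and notify the sponsor within 24 hours | No report needed | Conflict, clearest on notification |
| Grade 3 to 5 | 7.3: record it whatever the attribution | No report needed | Not reconciled |
| Fatal | 7.4.3: record it and report it as an SAE | No report needed | Conflict |
| Not serious, grade 1 or 2 | 7.3 asks for these only if at least possibly related | No report needed | No conflict |

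**Step 3. Is either rule written as an exception to the other?** No. Section 7.4.2 speaks of all and any SAEs and does not mention 7.5. Section 7.5.2 does not mention 7.4.2 and does not say that it limits only expedited reporting.

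**Step 4. Do the 7.5 definitions fit the population?** Take a patient whose only neoplasms are benign NF2 tumours. There is no previous malignancy, so the literal condition in 7.5.1 is not met, even for a cancer caused by selumetinib. The same holds for a cancer caused by earlier radiotherapy to a vestibular schwannoma, which section 3.1.7 permits if at least 6 months have passed. Such a cancer has no 7.5 category, or it drifts into the waived one. A patient with a true earlier cancer can be classified.

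**Step 5. What happens after the window?** The 7.4.2 period closes 30 days after treatment. Section 5.6 then provides two years of follow-up, which among adverse events names those related to selumetinib. Section 5.7.5 gives patients removed for progression 30 days of observation after the last dose. Any rule for later cancers would need its own stated window.

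**The case against.** The strongest reply is that 7.5 is standard oncology wording, read here too literally, and that other sections limit the damage. Much of this is right, and it rules out several stronger readings.

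- A reader might infer that a new cancer in an NF2 patient fits no SAE route. It does: 7.2.4 and 7.4.2 apply without reference to a prior malignancy.
- A reader might infer that 7.5 cannot classify NF2 patients at all. Section 7.5.1 names the investigational agent as an example of causative treatment, and 7.4.3 loosely calls the study disease a malignancy. The likely intent is that a cancer caused by selumetinib is reported. A serious suspected reaction is also caught by 7.4.2 and, if unexpected, by 7.6.2.
- A reader might infer that a cancer judged unrelated would vanish from the safety record. Sections 7.3 and 7.4.3 require grade 3 to 5 events and deaths to be recorded whatever the attribution. Section 7.5.2 waives reporting, and it is not clear that this waives recording. Section 12.4 also has the sponsor-investigator or a designee reviewing serious events as they occur.

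These points narrow the problem to cancers judged unrelated, and mainly to sponsor notification. They do not remove it. Intent is not text, and no section says that 7.5.2 yields to 7.4.2 or applies only to expedited reports. The definitions still rest on a prior malignancy that a typical participant need not have had.

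**Conclusion.** The point holds as an unreconciled inconsistency in the safety-reporting text. It covers a new cancer judged unrelated to earlier treatment that meets a 7.2.4 criterion or is grade 3 to 5, from day 1 to 30 days after treatment. The definitional defect is separate: it arises on a literal reading, for patients with only benign tumours.

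The size cannot be put as a number. The documents give no expected rate of new cancers, and a supposed count of missed cases would only illustrate a hypothetical event. The primary endpoints, the two-stage rules and their error rates are untouched.

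The conclusion assumes that reporting in 7.5.2 includes notifying the sponsor, and that no document outside the protocol ranks the two sections. It is worth correcting because the affected events are grave, the trial is uncontrolled, and the change is small.

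**What to change.** Rewrite 7.5 as follows.

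1. Delete the waiver in 7.5.2.
2. Define the event as any new malignancy, without reference to a prior one.
3. Treat it as an SAE (important medical event), recorded and notified under 7.4.2 regardless of attribution. Record attribution separately, on the scale in 7.1.
4. State the window. Either keep the 7.4.2 period of day 1 to 30 days after treatment, or set a separate period explicitly if later cancers are to be covered.
5. Say how malignant transformation of an NF2 tumour relates to 7.4.3, which exempts documented progression from SAE reporting unless it results in death.

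Within the existing window, this costs a rewritten short section and a clarifying sentence in 7.4.3. A longer window also means aligning 7.4.2, the follow-up text in 5.6 and the 30-day observation in 5.7.5, with some added data collection. Sample size and analysis do not change.

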7.6 Reporting

7.6.1 IRB Reporting Requirements:

CCHMC IRB Reporting Requirements: Unexpected and related adverse events will be reported to the CCHMC IRB per institutional policies. The sponsor-investigator will report any unexpected life threatening event or death (grade 4 or 5) adverse event to the CCHMC IRB within 7 calendar days after the sponsor is made aware of the event.

Reporting of Protocol Violations/ Deviations and Unanticipated Problems: Any protocol violations, deviations, or unanticipated problems should be documented and reported according to CCHMC policy.

7.6.2 FDA Expedited Reporting requirements for studies conducted under an IND: If the Sponsor-Investigator deems that an event is both a serious SAR AND unexpected, the Sponsor-Investigator is responsible for submitting the event to the IND (FDA) within 15 calendar days. If the Sponsor-Investigator is notified of an unexpected fatal or life-threatening SAR, the FDA is to be notified as soon as possible but in no case later than 7 calendar days after the Sponsor-Investigator's initial receipt of the information. A MedWatch Form 3500A will be completed and submitted to the IND (FDA) for expedited reporting requirements as outlined in 21 CFR 312.32. The MedWatch 3500a form can be accessed at http://www.fda.gov/Safety/MedWatch/HowToReport/DownloadForms/default.htm.

7.6.3 Reporting to Astra-Zeneca:

The IND Sponsor or designee will report all adverse events or adverse drug reactions subject to expedited reporting to Astrazeneca at the same time the report is submitted to the FDA. Astra-Zeneca will also be notified of unexpected, suspected serious adverse event to within 15 days.

8 AGENT INFORMATION

A list of the adverse events and potential risks associated with the investigational agent administered in this study can be found in Section 7

Selumetinib (AZD6244)

8.1.1 Agent Information

Chemical Name: 6-(4-Bromo-2-chloro-phenylamino)-7-fluoro-3-methyl-3H-benzoimidazole-5-carboxylic acid (2-hydroxy-ethoxy)-amide hydrogen sulfate\

Other Names: ARRY-142886; AR00142866; AR-142886-01); Selumetinib Classification: Mitogen-activated protein kinase (MEK) inhibitor

CAS Registry Number: 943332-08-9

Molecular Formula: C₁₇H₁₅BrClFN₄O₃ . H2SO4 M.W.:555.7

Mechanism of Action: The RAS/RAF/MEK/ERK pathway is an important mediator of many cellular processes including proliferation, survival, differentiation, apoptosis, motility, and metabolism. This pathway is often aberrantly activated in human tumors due to the overexpression of activated K-RAS, mutant b-Raf, or other growth factor receptors. Selumetinib

is a selective mitogen-activated protein kinase (MEK) inhibitor. By inhibiting MEK, selumetinib inhibits ERK phosphorylation. Thus, selumetinib may inhibit oncogenic growth signaling in tumor cells by targeting the RAS/RAF/MEK/ERK pathway.

Formulation: Selumetinib hydrogen sulfate capsules contain 10 and 25 mg of selumetinib (expressed as free base) supplied as a series of size 4, plain, hydroxypropylmethylcellulose (HPMC) capsules in white high density polyethylene (HDPE) containers with foil-lined, induction-sealed, child-resistant closures. Each bottle contains 60 capsules. May be replaced with most current formulations, as determined by Astra-Zeneca.

Each capsule contains a dispersion of selumetinib hydrogen sulfate in d- α -tocopheryl polyethylene glycol 1000 succinate (TPGS; a water soluble form of vitamin E).

Storage: Store the selumetinib hydrogen sulfate capsules at room temperature (20°C-25°C). Brief excursions are permitted between 15°C and 30°C. The temperature of shipments of 10mg capsules must also be monitored to ensure the temperature is within the required limits (below 30C). Data is available to support the 10mg capsule being stored at 30C or less and that performance could be reduced if stored at temperatures higher than 30C.

25mg capsules are stored at room temperature; however temperature monitoring is not necessary for 25mg capsules.

Stability: Stability studies are ongoing.

Availability: Selumetinib hydrogen sulfate capsules are provided to CCHMC by Astra-Zeneca

Route of Administration: Oral. Take selumetinib on an empty stomach either 1 hour before or 2 hours after meals and should be taken with water only.

Potential Drug Interactions: CYP3A4 is the predominant isoform responsible for selumetinib oxidative metabolism with CYP2C19, CYP1A2, CYP2C9, CYP2E1 and CYP3A5 involved to a lesser extent. *In vitro* studies indicate that selumetinib also undergoes direct Phase 2 metabolic reactions to form glucuronide conjugates principally involving the enzymes UGT1A1 and UGT1A3. Selumetinib is primarily metabolized by CYP1A2 to N-desmethyl AZD6244 which is 3-5 fold more pharmacologically active than Selumetinib but circulates at ~7% of the parent. Based on clinical trials, concomitant medications that are strong inhibitors/inducers of CYP3A4 or fluconazole (strong CYP2C19 and moderate CYP3A4 inhibitor) should be avoided, if possible. A list of medications with the potential for interaction with selumetinib is available in APPENDIX C.

In vitro, selumetinib is not an inhibitor of CYP1A2, CYP2A6, CYP2B6, CYP2C8, CYP2C9, CYP2C19, CYP2D6, CYP3A4 and CYP2E1. In vitro, selumetinib is not an inducer of CYP3A4, CYP1A2 and CYP2B6.

In vitro studies suggest that selumetinib does not inhibit the breast cancer resistance protein (BCRP), P-glycoprotein (P-gp), OATP1B1, OATP1B3, OCT2, OAT1, MATE1 and MATE2K at the recommended paediatric dose. A clinically relevant effect on the pharmacokinetics of concomitantly administered substrates of OAT3 cannot be excluded.

Based on *in vitro* studies, selumetinib is a substrate for BCRP and P-gp transporters but is unlikely to result in clinically relevant drug interactions at the recommended paediatric dose.

Vitamin E intake

Selumetinib capsules contain vitamin E in the form of TPGS, a water-soluble form of vitamin E, which acts as a formulation excipient. The maximum daily dose of vitamin E that a study subject may receive from selumetinib is approximately 270 mg/day. High doses of vitamin E have been reported to potentiate the anticoagulant activity of coumarins such as warfarin. Therefore, selumetinib should be administered with caution in patients who are also receiving concomitant coumarin anticoagulant medications. These patients should have their international normalized ratio [INR] monitored closely/ anticoagulant assessments conducted more frequently, and the dose of the anticoagulant should be adjusted accordingly.

In addition, the concomitant intake of supplemental vitamin E should be avoided in all subjects receiving selumetinib/placebo.

